4.0 Study Endpoints

Primary Research Question: Can taVNS stimulation be automatically triggered during 75% of the total time for active infant arm and trunk movements during CIMT? **Primary Outcome measure:** Percentage of treatment sessions where total stimulation time was 75% of total active movement time.

Limitations and alternative approaches: *Trialing EMG system:* We will trial the EMG sensor system first with two healthy infants in the CHP laboratory setting to trouble shoot set-up and connection issues. The BSL and CIMT team will make any necessary modifications to the EMG-taVNS set-up. *Comparing total movement time to total stimulation time does not ensure stimulation is being provided at the appropriate time:* The stimulation device changes color when stimulation is being provided. Therefore, a second 'recording' therapist can monitor if the screen is green('on') when also recording active movement.

Aim 2: To generate proof of concept evidence demonstrating ability to provide high fidelity CIMT+taVNS treatment in a home-based setting in 3 infants. We will have a second therapist videotape CIMT therapy sessions while the CIMT therapist is delivering taVNS in the home with EMG triggered taVNS. We will randomly score 20% of sessions for CIMT treatment fidelity with published CIMT Fidelity tool. This aim will be completed with the final 3 participants after EMG set-up is finalized with first 2 participants.

Secondary CIMT+taVNS feasibility outcomes: Ability of therapist to operate taVNS easily and successfully by earning a "meet or exceed" score (3 or 4) on random therapy sessions by CIMT Fidelity Instrument. Ability of infant to tolerate wired ear electrode while remaining securely in place during sessions.

Secondary CIMT +taVNS efficacy outcomes: Change in the functional motor outcomes pre and post intervention on the *Quality of Upper Extremity Skills Test (QUEST)*

Title: Extending taVNS Paired with Infant CIMT into a Home-Based Setting: Technology Development Requisite for a Randomized Trial

PI: [name]

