3.0 Intervention to be studied

General Methods for home-based delivery of taVNS +CIMT The goal of this discovery pilot project is to further develop the technical aspects of taVNS+CIMT delivery so that it is practical for delivery by a CIMT therapist in a home-based setting. This is essential to prepare for a treatment effectiveness study, which by necessity must be home-based because of the minimum 40-hour time commitment. First, we will use EMG sensors to automatically trigger the taVNS device, with the goal of decreasing the burden of treatment for the therapist. We will place the EMG sensors on major muscle groups on the shoulder and trunk and refine placement as needed to show that EMG-triggering can accurately and effectively trigger stimulation for 75% of total time spent in active movements. The therapist will still be able to manually trigger for other targeted behaviors (such as grasping). Once our placement of sensors has been tested and meets this designated threshold, the EMG-triggered system will be tested in home-based CIMT treatment.

The therapists providing the CIMT treatment are part of the study team. They have received specialized training in CIMT and the delivery of taVNS. These therapists were also a part of our original CIMT & taVNS study described above in section C1.2. They were part of the team who suggested the modifications of using EMG sensors to automate stimulation.

C2.1.1 Inclusion Criteria: Five 6–18 month-old infants, with hemiplegia/motor asymmetry qualifying for CIMT, Gross Motor Function Classification System (GMFCS) level I-IV, ability to maintain sitting position for 5 minutes with moderate assistance. **Exclusion Criteria:** Non-English literate parents, GMFCS level V, severe motor impairment/ quadriplegic involvement; uncorrected blindness or deafness, cardiomyopathy. Infants with cardiac issues will be cleared by cardiology before beginning treatment.

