C2.2.2 Targeted Muscle Groups We aim to automate 75% of stimulation time without significantly increasing the burden of system set-up/treatment delivery. We will use 2 sets of EMG sensors placed on the muscle groups activated in the vast majority of reaching and dynamic balance tasks.

- Reaching- Immature reaching in infants is initially driven by the biceps and triceps^{28,29}. As targeted reaching improves there is an increased use of the deltoids and upper trapezius as prime movers. Depending on the age/ability of the child we will target biceps brachii or anterior deltoid^{28,29}.
- Trunk control- EMG literature related to development of dynamic sitting balance indicates that thoracic level paraspinal muscles are most involved with emerging sitting balance and transitions to lumbar paraspinal activation as infants progress to more independent sitting balance²⁸⁻³⁰.

C2.2.3 Outcome measures for EMG automation taVNS stimulation is most effective when directly paired with active movements. Infant movement kinematics are characteristic of continuous movements rather than discrete movements. Since motions are not clearly discrete, we cannot count the number of stimulations and movements. Instead, a second therapist will record the time that the infant is actively engaged in movement tasks and compare that to the total time of taVNS stimulation, recorded by data acquisition modules in our taVNS set-up. One therapist will be delivering CIMT, a second therapist will be recording active movement time. For the first 2 participants, treatments will be completed in the research lab. This will allow the full team to be present, making sure that EMG triggered stimulation is occurring at the same time as active movement (the screen turns green when stimulation is on). If stimulation is not being delivered during active movement, modifications will be made to the system (e.g. changing amplification threshold for triggering, adjusting sensor location, etc). If total stimulation time is within 75% of total active movement time for therapy sessions in the first 2 infants, then we will transition CIMT delivery to the home-based setting for the final 3 infants.

C2.1.2 Treatment Delivery: CIMT-trained therapist with assistance from a research assistant will deliver CIMT for 40 hours (2 hours/day, 5 days/week for 4 weeks) +taVNS delivered via the BabyStrong (BS) system, (Soterix taVNS electric pulse generator unit & Neolead® electrodes).

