- 1) Hydrogel electrodes are placed in front of tragus and inner tragus/cymba chonchae, securing the wires behind head with tape. taVNS unit is attached to the baby using Velcro cummerbund (Fig.1, 2).

Title: Extending taVNS Paired with Infant CIMT into a Home-Based Setting: Technology Development Requisite for a Randomized Trial

PI: [name]

- 2) EMG electrodes will be placed on the shoulder (biceps/deltoid m) and on the trunk (paraspinus m) and connected to the taVNS unit via a wired interface.
- 3) CIMT and BSL therapists establish perceptual threshold (PT) daily, increasing slowly, until infant shows signs of tingling sensation. TaVNS is delivered at $0.1\text{mA} < \text{PT}$, $500\mu\text{sec}$, 25Hz, during each CIMT session, timed with movements of the weaker arm /trunk.
- 4) A CIMT therapist will deliver CIMT and use the manual trigger if needed for hand movements, while a second 'recording' therapist will record the active movement time. The Data Acquisition (DAQ) interface will record the amount of stimulation time and intensity from both EMG and manual triggering.
- 5) Good, moderate or poor impedance is constantly displayed on the taVNS unit. With poor contact, a beep sounds, and the electrode is adjusted.
- 6) Parent and OT will answer weekly questionnaire to assess their perception of ease of use, infant tolerance, and any recommendations for improvement of taVNS system or delivery.

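### The 75% target is set for EMG-triggered stimulation, but the primary outcome and the C2.2.3 lab-to-home rule score total stimulation time, from which manual triggering is not excluded

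*Combined protocol and SAP*

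**What the plan says.** **The target concerns automatic triggering.** The primary question in Section 4.0 is "Can taVNS stimulation be automatically triggered during 75% of the total time for active infant arm and trunk movements during CIMT". Aim 1 in Section 1.0 sets the same goal for EMG, as at least 75% of active arm and trunk movement time. The general methods in Section 3.0 aim to show that "EMG-triggering can accurately and effectively trigger stimulation for 75% of total time spent in active movements", and Section 10.0 repeats this.

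**The scored quantity is a total.** The primary outcome in Section 4.0 is "Percentage of treatment sessions where total stimulation time was 75% of total active movement time". Section 3.0, C2.2.3, makes the move to the home depend on the same kind of total: "If total stimulation time is within 75% of total active movement time for therapy sessions in the first 2 infants".

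**The total has two possible sources.** Under C2.2.3 a second therapist times active movement, and the team will "compare that to the total time of taVNS stimulation, recorded by data acquisition modules in our taVNS set-up". Step 4 of C2.1.2 says the DAQ interface will "record the amount of stimulation time and intensity from both EMG and manual triggering". The same step lets the CIMT therapist "use the manual trigger if needed for hand movements". The general methods and Section 10.0 also keep the manual trigger available, with grasping as the example.

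**No exclusion is stated.** No supplied section removes manual time from the total. The analysis plan in Section 12.0 deals with motor scores and gives no scoring rule for the primary outcome.

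**The condition for moving home is worded in two ways.** The general methods and Section 10.0 tie it to the sensors meeting the EMG threshold. C2.2.3 ties it to total stimulation time.

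**The concern.** Section 2.0 explains that the project exists because a setup triggered by the therapist will not work in the home. The primary result should therefore show how much of the triggering the EMG system does by itself. If time from the therapist's button counts towards the 75%, a session can be scored as a success when EMG fell short, and the more the therapist steps in, the easier the criterion is to meet.

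Two things depend on this: the reported percentage of successful sessions, and the C2.2.3 decision to move home after the first two infants.

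**Working it through.** The plan states no expected success rate, power or error rate for this outcome, so there is no figure of its own to reproduce. The schedule does check: 2 hours x 5 days x 4 weeks = 40 hours, as stated. That is 5 x 4 = 20 sessions per infant, 2 x 20 = 40 in the lab stage, and 5 x 20 = 100 if all five infants complete and are counted.

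**Definitions, per session**
- A = active movement time (second therapist's record).
- E = EMG-triggered stimulation time (DAQ).
- M = time stimulated by the manual trigger alone (DAQ). Seconds with both triggers on belong to E.
- m = M / A. The documents give no value, so 0 to 0.30 is an assumed range.

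**Criterion as worded**, reading the 75% as a minimum: (E + M) / A >= 0.75.

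**Criterion the question implies:** E / A >= 0.75.

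**Lowest EMG ratio that passes as worded:** E / A = 0.75 - m.

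| Assumed manual-only share m | Lowest passing E / A |
|---|---|
| 0 | 75% |
| 0.10 | 65% |
| 0.20 | 55% |
| 0.30 | 45% |

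**Example with assumed minutes:** A = 60, E = 36, M = 9.
- As worded: (36 + 9) / 60 = 75%, a success.
- EMG only: 36 / 60 = 60%, not a success. An EMG-only pass needs 0.75 x 60 = 45 minutes.

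**Denominator.** Aim 1 and the primary question refer to arm and trunk movement. The general methods, C2.2.3, the primary outcome and Section 10.0 refer to active movement without that limit. In the same example, suppose 12 of the 60 active minutes are hand movement only and all EMG time falls in arm or trunk movement. The EMG ratio is then 36 / (60 - 12) = 75% instead of 60%. Conversely, if the shoulder and trunk sensors stay silent during hand-only activity that takes a share h of active time, and EMG fires only during active movement, the EMG ratio on all active movement cannot exceed 1 - h. That is below 75% once h exceeds 25%. The documents give no value for h.

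All of these are ratios of totals. They do not show that stimulation coincided with movement, a limit that Section 4.0 itself acknowledges.

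**The case against.** The strongest reply is that an EMG-only numerator is obviously meant. The outcome comes directly after a question about automatic triggering, and the C2.2.3 rule stands under a heading about EMG automation, beside text on adjusting sensors and trigger thresholds. Manual triggering is described as an exception for hand movements, while the sensors cover muscles used in most reaching and balance tasks. In the lab, the whole team also watches that EMG-triggered stimulation coincides with movement.

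Much of this stands. The intent is plausible and manual time may be small. But the text that defines the measure still says total stimulation time. The screen colour shows that stimulation is on; the documents do not say that it shows the source. Watching in the lab does not alter the ratio that is scored.

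A reader might infer more than the documents support:
- *That the outcome cannot answer the primary question.* This depends on manual use. With none, the two criteria agree.
- *That the plan accepts EMG triggering for 56% of active time.* This multiplies the 75% of active time by the C2.2.2 aim of automating 75% of stimulation (0.75 x 0.75 = 0.5625). The documents never combine the two, and the second may be a loose restatement of the first.
- *That the study could move home on manual time alone.* C2.2.3 read by itself would allow it, but the general methods and Section 10.0 require the EMG threshold. Sections 1.0 and 6.0/7.0 only summarise the sequence and do not contradict that condition.
- *That the DAQ cannot separate the sources.* Step 4 of C2.1.2 can be read as separate recording. It does not say so outright, which calls for a check, not a conclusion.

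**Conclusion.** The mismatch between the primary question and the primary outcome is real as the text stands, and the C2.2.3 rule shares it. Whenever manual-only time makes the difference, the written rule scores a session as a success although EMG missed its target. At the threshold the shortfall equals the manual-only share of active time, point for point. Its actual size is unknown and may be zero.

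This rests on reading the 75% as a minimum, on the DAQ total including both sources as step 4 indicates, and on the supplied text, part of which was removed before review. Confidence is high for the wording gap but does not extend to its effect. In a five-infant pilot without a powered test, the harm is to the interpretation of feasibility, not to error rates. It still needs correcting before the first session, because it concerns the primary outcome.

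**What to change.** 1. In Sections 3.0 (C2.2.3) and 4.0, define the numerator as EMG-triggered stimulation time from the DAQ, excluding seconds delivered by the manual trigger alone. State the threshold as at least 75%, as Aim 1 does, in place of *within* 75% (C2.2.3) and *was* 75% (Section 4.0).
2. Use this one measure for the primary outcome and the C2.2.3 rule, and reconcile that rule with the general methods in Section 3.0 and with Section 10.0.
3. Before the first session, have the sponsor state one denominator that matches the primary question, including how hand-only time is treated.
4. Report manual and total stimulation time separately.
5. Confirm beforehand that the DAQ log separates the two sources, including seconds when both are on.

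The cost is a few wording changes and one check of the log. The numerator change needs no new data if the log separates the sources. An arm-and-trunk denominator would require hand-only time to be told apart reliably. The downside is that the reported success rate may be lower, more so if hand-only time stays in the denominator.

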to trigger stimulation. Placing EMG sensors over key muscles in the shoulders and trunk we allow us to automatically detect when an infant is reaching or using their trunk to work on activities like sitting or rolling. By using EMG sensors we should be able to pair stimulation with movements reducing the burden on the therapist and allowing them to focus on facilitating a high quality treatment session. Automating the stimulation would make taVNS-paired CIMT more achievable in the home-based CIMT programs. Home-based delivery of CIMT is considered best practice for pediatric clients so families can be fully engaged, burden for families is reduced, and new skills can easily transfer to the natural environment for better carry over of treatment.

Qualifications

We have a unique collaboration of experts in brain stimulation, pediatric brain injury, translational clinical science and pediatric occupational therapy in this pilot project, and we are one of the few groups able to rapidly translate this neuromodulatory modality into home-based CIMT services. Refining the treatment protocol for home-based taVNS+CIMT and trialing incorporation of reliable taVNS triggering by this device we will provide us strong data to submit a grant for a randomized trial of home delivered taVNS+ CIMT in infant hemiplegia.

Study Aims

Aim 1: Investigate the feasibility of incorporating automatic triggering of the taVNS device using EMG sensors. *Rationale:* Manual taVNS triggering is mentally taxing for a therapist providing intensive, CIMT intervention. Movement based triggering would decrease the mental effort for using taVNS allowing the therapist to focus more on the treatment session. *Aim specific methods:* We will systematically test key muscle groups to see if EMG can be used to trigger taVNS stimulation at least 75% of the total time for active infant arm and trunk movements during CIMT. The first 2 participants will be completed in clinic to allow for updates to EMG system real time. After the first 2 participants complete the study we will trial the EMG system in the home setting for Aim 2.

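### The primary outcome counts sessions at a 75% cut and names no required share of sessions, while the primary question and Aim 1 set the target as a share of active movement time

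*Combined protocol and SAP*

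**What the plan says.** Section 4.0 asks: "Can taVNS stimulation be automatically triggered during 75% of the total time for active infant arm and trunk movements during CIMT"? Aim 1 in Section 1.0 supplies the direction; the plan there is to see whether EMG can "trigger taVNS stimulation at least 75% of the total time for active infant arm and trunk movements during CIMT". Sections 3.0 and 10.0 repeat the development goal on the same scale: EMG should "accurately and effectively trigger stimulation for 75% of total time spent in active movements". All of these are shares of movement time.

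The primary outcome measure in 4.0 is on a different scale: "Percentage of treatment sessions where total stimulation time was 75% of total active movement time". It counts sessions, and it does not say at or above. Neither 4.0 nor the statistical paragraph in 12.0 states what percentage of sessions would count as success. Section 12.0 gives an analysis for the functional scores only, and says that a power analysis for the primary outcome is not valid with 5 participants.

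The one decision rule is the lab-to-home gate in C2.2.3: "If total stimulation time is within 75% of total active movement time for therapy sessions in the first 2 infants", treatment moves to the home for the last three. This is a time ratio, and it leaves open whether each session or a total over sessions must meet it.

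Two details concern the numerator. Under C2.1.2, item 4, the data acquisition interface will "record the amount of stimulation time and intensity from both EMG and manual triggering", so recorded stimulation time includes manual triggering. C2.2.2 uses yet another denominator: "We aim to automate 75% of stimulation time".

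**The concern.** The question is about how much movement time is accompanied by automatic stimulation. The outcome first turns each session into a yes or no at 75% and then reports the percentage of yes sessions. A session at 74% counts the same as one at 10%. The result therefore mixes two things: the typical ratio, and how much the ratio varies between sessions. A reader given only the session percentage cannot recover the ratio that the question asks about, and has no stated mark against which to read the percentage.

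This is the primary outcome of a pilot meant to support a grant application for a randomized trial. The number carried into that application should answer the question that the pilot poses.

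**Working it through.** **Inputs from the documents.** Section 3.0 (C2.1.2) gives 2 hours a day, 5 days a week, for 4 weeks: 2 × 5 × 4 = 40 hours, which matches the stated total. That is 5 × 4 = 20 sessions per infant. With up to 5 infants (6.0 & 7.0) there are up to 100 sessions, 2 × 20 = 40 in the lab and 3 × 20 = 60 at home. The plan gives no pass mark, SD, alpha or power for the primary outcome, so there is no figure of its own to reproduce.

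**Assumptions.** The outcome is read as at least 75%, as in Aim 1. The between-session SD is not in the documents, so a range is shown.

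**Step 1: share of sessions passing, normal spread.** P(session ratio ≥ 75) = 1 − Φ((75 − mean)/SD).

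| Mean ratio | SD 3 | SD 5 | SD 10 | SD 15 |
|---|---|---|---|---|
| 70% | 5% | 16% | 31% | 37% |
| 75% | 50% | 50% | 50% | 50% |
| 80% | 95% | 84% | 69% | 63% |
| 85% | 100% | 98% | 84% | 75% |

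For a mean of 80% and SD 3, (75 − 80)/3 = −1.67, giving 95%; at SD 15, (75 − 80)/15 = −0.33, giving 63%. The same mean gives very different session percentages. The converse also holds. Mean and SD pairs of 78 and 3, 80 and 5, 85 and 10, and 90 and 15 all lie one SD above the cut, so all report 84% of sessions.

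**Step 2: other shapes, mean ratio fixed at 75%.**
- Any symmetric continuous distribution: 50%.
- Beta (ratio capped at 100%), with k = 0.75 × 0.25/SD² − 1 and parameters 0.75k and 0.25k: 51% at SD 0.03, 54% at SD 0.10, 61% at SD 0.25.
- Lognormal (ratio can exceed 100%), with s = √ln(1 + CV²) and P = 1 − Φ(s/2): 49% at CV 0.05, 42% at CV 0.40.
- Constructed extremes: sessions at either 76% or 50% give (75 − 50)/(76 − 50) = 96%; sessions at either 100% or 74% give (75 − 74)/(100 − 74) = 4%.

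**Step 3: sampling range.** In a simulation of 5 infants × 20 sessions with a true mean of 75% and a within-infant SD of 10 points, the observed session percentage has a 95% range of 40% to 60% if infants do not differ. The range is 24% to 76% if infant means also vary with SD 10.

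**Step 4: what the gate's ambiguity means.** Take a mean of 80%, independent sessions and a stable system. If all 40 lab sessions must reach 75%, the chance of passing is 0.841⁴⁰ ≈ 0.001 at SD 5 and lower at SD 10. If the average over the 40 sessions must reach 75% (equal movement time per session), then at SD 10 the standard error is 10/√40 = 1.58, z = 5/1.58 = 3.16, and the chance is about 0.999. The two readings of one sentence give opposite decisions.

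**The case against.** The strongest defence is that neither Aim 1 nor 4.0 says on average. If 75% is meant as a floor for each session, the percentage of sessions reaching it is a fair measure of reliability for a device intended for home use. A system averaging 75% is then not on target, and a pass rate near 50% would correctly show unreliable performance. This stands as far as it goes, and it is why the session percentage should be kept. It does not supply the missing mark: under that reading the plan still has to say what percentage of sessions is enough.

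It can also be said that the missing direction is editorial, since Aim 1 states it. That is fair for the wording alone.

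A further caution concerns any replacement. The documents describe two totals, stimulation time from the device and movement time from the second therapist. Section 4.0 itself concedes that comparing totals does not show that the two coincide; its remedy is that the second therapist watches the screen. No time-aligned record is described. A ratio of totals can exceed 100% if EMG fires outside active movement, and pooled minutes would then let over-triggered sessions make up for failed ones. This stands and shapes the fix.

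Three stronger readings are tempting, and the documents do not support them:
- **An on-target system scores 50%.** This needs a symmetric spread around 75% and a target read as an average. The documents give neither.
- **Any result could be called feasible.** The C2.2.3 gate is a time-ratio criterion, and 3.0 and 10.0 make home testing depend on meeting the threshold. The rule is loose, but it exists.
- **The cut loses a known fraction of the information.** The usual efficiency figures assume independent sessions with a known SD. Here sessions are clustered in up to 5 infants, the system may be modified during the lab phase, and no test or interval is planned for this outcome.

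**Conclusion.** The point holds in a limited form. The primary outcome is not on the scale of the primary question, no share of sessions is named as a yes, and the only decision rule is a time ratio for the first two infants that does not say how sessions combine. These facts can be read directly from the text.

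The numerical size is illustrative because it rests on an assumed between-session SD. What does not depend on any one SD is that the session percentage cannot be translated back into a time ratio without knowing the spread. This should be corrected before the outcome is reported. It does not put the design of a five-infant technology pilot in doubt.

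**What to change.** - **Primary summary (4.0).** Use the ratio of EMG-triggered stimulation time to active movement time, per session and per infant, with its spread and with lab and home infants shown separately. Judge it against at least 75%.
- **Supporting summary.** Keep the percentage of sessions at or above 75%.
- **Manual triggering.** Report manually triggered time separately, since the question is about automatic triggering.
- **Labelling.** Call the measure a ratio of totals, not coverage, unless time-aligned records exist. Flag sessions above 100% so that over-triggering cannot offset failed sessions when minutes are pooled.
- **Wording.** In the outcome definition in 4.0 and in the gate in C2.2.3, say at least 75%, to match Aim 1. State in C2.2.3 whether the gate applies to each session or to each infant's total.

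The cost is small: a change of endpoint wording, plus separating EMG from manual time in the device output. The documents say that both are recorded but not whether they are stored separately, so that should be confirmed first.
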